This pilot study will utilize a single blind, placebo-controlled, randomized, repeated measures experimental design. Participants will be asked to come in for two visits at least 7 days apart. If study procedures are not completed in the two sessions (such as due to equipment malfunction or unexpected time restrictions/events), an additional session may be required to complete procedures. This will be scheduled at the participant's convenience. Participants will be asked to wear comfortable, casual clothing for participation ahead of time, during their phone screening. In the first visit, participants will be asked to complete a demographic health and function questionnaire. Questions may address their injury level, medical history, impact of their condition on physical functioning, breathing function, and their walking or other functional abilities. Participants may then be asked to undergo standardized assessments of muscle strength and sensory function. Following collection of this baseline information, the remainder of the first visit will be similar to all subsequent visits. Visits will include:

- Pre-assessments of respiratory strength, postural strength and function, EMG of trunk muscles, and trunk positioning using non-invasive sensors. For subjects who can stand or walk with assistance, ambulation assessments may be conducted while also recording trunk and lower extremity EMGs, and joint angles or forces using non-invasive sensors.
- 15 short exposures to hypoxic air, or a sham exposure, in a randomized order (details below)
- Post-assessments of respiratory strength, postural function, ambulation, EMG of trunk muscles, and trunk and joint positioning using non-invasive sensors

Each session will last about 3 hours and no longer than 6 hours. Rest breaks will be provided at regular intervals and at any time the participant requests. A study clinician will oversee the study procedures and monitor the participants, including a baseline assessment of vital signs (blood pressure, heart rate, and blood oxygen saturation) for safety.

For participants who provided consent for photography and/or video, recordings or photographs may be obtained during their session. Recordings or photographs will only occur based on the consent provided by each participant. The participant will be informed that they may refuse the use of photography or video recordings at any time during the procedures.

Study Procedures

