Subjects will rest and be asked not to ingest any food or drink other than water for 30 minutes after the delivery of acute intermittent hypoxia, because fullness of the stomach may impede full depression of the diaphragm and compromise maximal respiratory measures. Following this, maximal inspiratory pressure, maximal expiratory pressure, forced vital capacity, mouth occlusion pressure, postural strength assessments, Neuromuscular Recovery Scale components, and assessments of ambulation will be reassessed as outlined above. EMG electrodes, electrogoniometers, and pressure sensors will be worn during the acute intermittent hypoxia and rest period, and will be removed following the conclusion of all testing.

Following the procedures for each visit, a \$75.00 gift card or check will be provided to participants. Thus, upon full completion of two visits, subjects will have been provided with \$150.00 following their participation in the study. If participants are asked to come in for a third session, an additional \$75.00 will be provided.

No standard therapies for people with SCI currently include acute intermittent hypoxia. Thus, this research does not intend to directly deliver therapeutic benefits to subjects. Rather, this research seeks to determine the therapeutic potential of acute intermittent hypoxia on respiratory strength and postural muscle function for people with SCI. As an alternative to participating in this study, subjects may not enroll or choose to withdraw at any time.

Statistical Plan

Percent changes in maximal inspiratory pressure, maximal expiratory pressure, forced vital capacity, mouth occlusion pressure, EMG parameters, spine and hip angles, postural strength measures, absolute Neuromuscular Recovery Scale scores, and assessments of ambulation will be compared pre- and post-intervention for both experimental conditions. Changes for each subject will be averaged, and the group mean change \pm standard deviation will be reported and compared across experimental conditions. Statistical differences between the group means for each variable in each experimental

condition will be compared using t-tests. Multiple comparisons will be accounted for. Statistical analyses will be carried out by the study investigators.

Acute Intermittent Hypoxia Safety Profile

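### The two-visit comparison uses t-tests without a visit term and no balanced order is stated: a minor point, and cheap to improve

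*Combined protocol and SAP*

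**What the plan says.** The Overview in section 6 (Research Plan) sets out the design: "This pilot study will utilize a single blind, placebo-controlled, randomized, repeated measures experimental design". There are two visits with a minimum gap of a week. Each visit has a pre-assessment, then "15 short exposures to hypoxic air, or a sham exposure, in a randomized order (details below"), then a post-assessment. The later text on delivering hypoxia or sham covers gas, timing and equipment. It gives no method of generating the order, no ratio and no balance. Planned enrolment is 30.

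The Statistical Plan, also in section 6, works with pre-to-post changes, as percentages for most outcomes: "Changes for each subject will be averaged, and the group mean change" is reported with its standard deviation. It then says: "Statistical differences between the group means for each variable in each experimental" "condition will be compared using t-tests". No visit, period or sequence term appears there or elsewhere, and no sensitivity analysis or confidence interval is planned.

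**The concern.** With two visits and two conditions, each participant's hypoxia-minus-sham difference contains the condition effect plus or minus any visit difference in the pre-to-post change. The sign depends on which condition came first. A t-test without a visit term leaves that component in the residual error. If more participants start with one condition than the other, part of it also enters the estimate.

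A visit difference is plausible. The first visit adds a questionnaire and may add strength and sensory examinations. The respiratory tests depend on effort and may be repeated up to ten times each. The safety monitoring text says that testing could tire some participants. At stake is the precision of the condition comparison in a 30-person pilot and, for the one order list actually drawn, some displacement of its estimate.

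**Working it through.** **Inputs from the documents.** 30 participants; two visits; randomised order with no stated balance; t-tests on changes. The plan gives no effect size, SD, alpha or power, so it has no figure to reproduce.

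**Assumptions.** All 30 complete; two-sided alpha 0.05; SD of one condition's change 20 points; correlation between a participant's two changes 0.3; true effect 10 points; visit shift s (visit 2 change minus visit 1 change) of 0, 3, 6 or 12 points.

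**Model.** Let D be the hypoxia-minus-sham difference in change, and x = +1 if hypoxia came second, −1 if first. Then D = effect + s·x + error.

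- SD of the error in D = 20 × √(2 × (1 − 0.3)) = 23.7, a variance of 560.
- With no shift, SE = 23.7/√30 = 4.32. The noncentrality is 10/4.32 = 2.31, and power from the noncentral t is 60.9% (29 df). With the visit term at 15/15 it is 60.8% (28 df).

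**Balanced order, 15/15.** The estimate is not displaced. Without the term the expected variance of D is 560 + (30/29)s², which is 569, 597 and 709 at s = 3, 6 and 12. Simulation (40,000 trials per cell) gives:

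| Visit shift | Power, no term | Power, with term | 95% CI half-width, no term | With term |
|---|---|---|---|---|
| 0 | 61% | 61% | 8.8 | 8.8 |
| 3 | 60% | 61% | 8.8 | 8.8 |
| 6 | 59% | 61% | 9.0 | 8.8 |
| 12 | 51% | 61% | 9.9 | 8.8 |

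The half-width is used here only to measure precision. The gain is 0 to 1 point of power at s = 3, 2 to 3 at s = 6 and about 10 at s = 12.

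**Uneven order.** The unadjusted estimate moves by s × |n1 − n2|/n, where n is the number analysed. At 10/20 this is s × 10/30, or 1, 2 and 4 points at s = 3, 6 and 12. Conditional on that split, the size of the unadjusted test is about 5%, 6.5% and 10%; with the term it is about 5% throughout.

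**How likely is an uneven split?** Under simple randomisation of 30, exactly 15/15 has probability 14% and 10/20 or worse has 9.9%. Averaged over all splits, the unadjusted paired test keeps its size (4.9 to 5.2%).

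**Cost of the term without balance.** Under simple randomisation with no shift, power falls from 60.9% to 59.3%, a loss of 1.6 points. At s = 3 the loss is 0.8. At s = 6 the term gains 1.1 points, and at s = 12 it gains 8.

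**The case against.** The strongest reply is that this is close to a preference. Outcomes are changes from a same-visit pre-test, so a difference in level between visits largely cancels. The protocol states that "the remainder of the first visit will be similar to all subsequent visits"; the extra first-visit examinations are optional and come before the pre-test, and rest is provided. If the shift is 0 to 3 points, the term gains at most about 1 point of power with a balanced order and loses 1 to 2 without balance. All of this stands, and it keeps the point minor. What remains is that only one order list will be drawn, nothing in the plan stops it being uneven, and the remedy is nearly free.

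Three stronger readings are tempting, and the documents support none of them.

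- **The comparison is biased or its size is wrong.** Over the randomisation the paired test has neither fault. Displacement arises only given an uneven split and a real visit difference in the change.
- **The test is unpaired.** The wording about group means might suggest it, and pairing is not stated. But a repeated-measures design and changes taken for each subject make a paired test the natural reading.
- **Carryover.** Section 8 (Possible Benefits) expects responses to have gone within four hours, against a gap of a week or more.

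**Conclusion.** The point holds as a minor, inexpensive improvement in precision and robustness, not as a validity failure. The plan specifies t-tests with no visit term and states no balance of order. Under the assumed values the loss is 0 to 3 points of power for shifts up to 6 points at 15/15. It reaches about 10 points only at a 12-point shift, which exceeds the assumed effect and has no support in the documents. An uneven order matters more for the estimate: 1, 2 or 4 points at 10/20. The SD, correlation, effect and visit shift are all assumptions. The form of the displacement, shift × imbalance/n, does not depend on the first three.

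**What to change.** Make both changes together, because the term without a balanced order costs 1 to 2 points of power when there is little or no visit difference.

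**Statistical Plan.** Replace the t-test sentence with:

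> For each participant the hypoxia-minus-sham difference in pre-to-post change will be regressed on order (+1/−1); the intercept, with 95% CI, is the condition effect. Order is coded by the sequence of the sessions whose data are analysed.

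This makes the within-person comparison explicit. The coding rule is needed because the Overview allows that "an additional session may be required to complete procedures".

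**Overview.** Add:

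> Order will come from a concealed, balanced list (for example 15 hypoxia-first and 15 sham-first in random sequence).

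A balanced list does not guarantee balance among those analysed. The protocol accepts that "subjects may not enroll or choose to withdraw at any time", and the ambulation tests cover only participants able to attempt them. That is a further reason to keep the term.

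**Cost.** Two short text changes and an allocation list; one degree of freedom (60.9% to 60.8% power at 15/15 with no shift); and some predictability of order near the end of the list for anyone who knows the earlier allocations. No extra participants or data are needed.
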